17.2 Premature termination of the study

In the event that the Trial Steering Committee or Sponsor recommends early termination of the study for any reason, the Chief Investigator will notify the REC and will be responsible for informing participants of the premature termination of the study.

18 DATA MANAGEMENT

PenCTU will oversee the data management processes for quantitative data collection measures. The qualitative lead at each site will be responsible for management of qualitative data. All transcript data will be stored on the University of Liverpool's managed network server.

18.1 Subject numbering

Each participant will be allocated a unique trial number generated by computer following consent and will be identified in all study-related documentation by their trial number. A record of names, addresses and telephone numbers linked to participants' trial numbers will be stored securely for administrative purposes on the study database.

18.2 Data collection

Data will be recorded on study specific data collection forms (CRFs) at the study visits by the researcher. Participants will complete participant related outcome measures. Data will be collected on paper. All persons authorised to collect and record study data at each site will be listed on the study site delegation logs, signed by the relevant PI. A 20% random selection of anonymised CAB records of intervention participants will be checked against the debt advice protocol to check fidelity.

18.3 Data entry

Completed CRFs will be checked and signed at the research site before being sent to the CTU. Original CRF pages and questionnaires will be posted to the CTU at agreed time points for double-data entry on to a password protected database. Forms will be tracked using a web based trial management system. Double-entered data will be compared for discrepancies using a stored procedure. Discrepant data will be verified using the original paper data sheets.

18.4 Data confidentiality and security

The research teams will ensure that participants' anonymity is maintained on all documents. Data will be collected and stored in accordance with the Data Protection Act, 1998. Electronic records will be stored in a SQL Server database, stored on a restricted access, secure server maintained by Plymouth University. The website will be encrypted using Secure Sockets Layer (SSL). Direct access to the trial data will be restricted to members of the research team and the CTU, with

access granted to others on request. Access to the database will be overseen by the CTU data manager and trial manager.

18.5 Archiving

Following completion of trial data analysis, the Sponsor will be responsible for archiving the study data and essential documentation in a secure location for a period of 10 years after the end of the trial. No trial-related records should be destroyed unless or until the Sponsor gives authorisation to do so. Medical case notes containing source data or other trial-related information should be identified by a label "Keep until dd/mm/yyyy" where the date given is 15 years after the last participant's final study visit.

19 DATA MONITORING AND QUALITY ASSURANCE

The RA or other member of the research team will check any researcher-completed data collection forms for missing data or obvious errors before the forms are sent to the CTU. Data will be monitored centrally for quality and completeness by the CTU and every effort will be made to recover data from incomplete forms where possible. The CTU data manager will oversee data tracking and data entry and initiate processes to resolve data queries where necessary. The trial manager will consider and implement central and local monitoring strategies as appropriate.

All trial procedures will be conducted in compliance with the protocol and according to the principles of Good Clinical Practice. Procedures specifically conducted by the CTU team (e.g. randomisation and data management) will be conducted in compliance with CTU standard operating procedures (SOPs). As necessary, the Principal Investigators and the participating GP surgeries will be required to permit delegated member of the research team or sponsor representative to undertake trial-related monitoring to ensure compliance with the approved trial protocol, providing direct access to source data and documents as requested.

20 TRIAL OVERSIGHT

20.1 Trial Management Group

The Trial Management Group will oversee the day to day conduct of the trial including study planning, ethics submissions, contractual agreements and issues, monitoring recruitment, preparing relevant progress reports, organising steering committee meetings, monitoring any serious adverse events and being responsible for the Trial Master File and administration of the trial budget. The trial management group members will include the CI, the local PIs from each site/representative from each site, the CAB lead, the PPI lead, the trial health economist, the trial statistician, PenCTU data manager, a qualitative lead and the trial manager. Invited observers will include a representative of the CRN. Trial management meetings will take place on a monthly basis initially, moving to bi-monthly or quarterly meetings in the main trial phase of the study if appropriate.

20.2 Trial Steering Committee

The Trial Steering Committee will oversee the conduct, progress and safety of the trial and will provide advice to the Trial Management Group. Terms of reference for the TSC will be developed and forwarded to the study sponsor. The TSC will include the CI, an independent trial statistician,

an independent health economist and a service user representative. The committee will include an independent chair. Invited observers will include the trial statistician, the trial health economist, trial manager and a representative from the research sponsor. The Trial Steering Committee will meet at the beginning of the trial, at the end of the internal pilot trial and thereafter as required, at least annually.

21 STATISTICAL CONSIDERATIONS

21.1 Sample size

We require 135 patients/arm to have 90% power to detect a clinically meaningful difference in the primary outcome of 3.5 BDI units between groups at 5% two-sided alpha (based on standard deviation (SD) of 9)^{xiv, xv}. Given our analysis of covariance analysis approach to data analysis (see below) this sample size is likely to be conservative. To allow for a cluster allocation, we need to inflate the sample size by a design effect of 1.45 (assuming an intracluster correlation coefficient (ICC) of 0.05 and average cluster size of 10)^{xvi}. In the pilot trial, we will recruit and randomise 120 patients to intervention and control arms nested by individual or cluster randomisation. If the pilot trial demonstrates no strong evidence of contamination (see section 8.2), main trial allocation will proceed at an individual level and we will require a total of 195 patients/arm across both pilot and main trials (allowing for 20% attrition and clustering in pilot trial). If pilot demonstrates strong evidence of contamination, full trial allocation will proceed at a practice level and we will require a total of 235 patients/arm across both pilot and main trials (allowing for 20% attrition and clustering in pilot and full trial). Should the level of outcome clustering within and between practices be higher (i.e. an ICC of 0.10) these sample sizes will provide 80% power (at 5% alpha).

21.2 Statistical analysis

As the trial protocol (other than the method of allocation) will remain consistent across pilot and main trial, outcome data from both trials will be aggregated into a single data analysis at the end of the main trial:

The primary analysis will compare primary and secondary outcomes at 12 months according to the intention-to-treat principle i.e. according to random allocation. Regression based analyses will adjust for baseline score and take account of data clustering. Outcomes will be analysed by locality to explore any effects on outcomes of CAB advisor approach regionally. Secondary analyses will be undertaken with repeated measures comparison of outcomes at both 4 and 12 month follow up time points. Sensitivity analyses will be undertaken to examine the effects of missing data and differing imputation strategies. Interaction analyses will explore the potential impact of a limited number of pre-specified (moderator variables) subgroups (i.e. severity of depression (BDI <20 v rest), severity of debt- priority v non-priority, employed v unemployed, and hopelessness rating) as interaction terms. If there is a switch to individual randomisation after pilot, we will implement minimisation on the variables: severity of depression (i.e. BDI <20 vs >=20); severity of debt (priority vs non priority); employment status (employed vs unemployed); and level of hopelessness. If after pilot, it is decided that we need to go with cluster randomisation, then we will not implement this minimisation. No interim analyses are planned.

Contemporary mediational analysis methods will be used to explore the impact of treatment adherence/non-attendance and potential causal mechanisms^{xvii}. A full statistical analysis plan will be developed before the end of data collection and agreed with the TMG and TSC in accord with CONSORT recommendations.

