11 RANDOMISATION

In the internal pilot trial, relevant GP practice demographic information will be sent to CTU/study statistician by CRN in England, this activity will be supported by ABMU Health Board in Wales. Four practices (matched on their size and deprivation index score) in each of the three trial localities will be randomised to intervention or control arms and cluster (practice) or individual (patient) level allocation such that six practices are randomised to cluster allocation and six practices to individual allocation. To achieve total population research practice sites may be combined using a hub and spoke approach where available. The randomisation sequences and matching will be computer generated undertaken by an independent statistician working with the CTU. The CTU programming team will run checks before and during the trial to verify the integrity of the randomisation system.

Should the internal pilot show contamination to be a problem, for the main trial, the remaining practices will be randomised to intervention or control stratified by size and the deprivation (higher vs lower) of the populations they serve. If contamination is not found to be a problem, participants would be individually randomised to intervention or control.

Additional practices for the main trial will be identified and recruited once a decision has been made at the end of the internal pilot whether randomisation will be individual or cluster.

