22.1 Piloting the intervention

The proposed intervention is a complex intervention and will therefore need to be piloted. The four organisational elements are well established and it is not anticipated that there will be major theoretical changes to the intervention; however, it is recognised firstly that adaptations will be required and secondly that a detailed implementation process will be needed to ensure the intervention is delivered optimally. Fidelity will be assessed and qualitative interviews will be used to assess implementation problems and facilitators, and problems resolved to ensure the intervention is implemented as closely to the model as possible. Refinements to training and the manual may be made to help ensure fidelity to the original model. During the main trial the intervention will continue to be implemented with any additional procedures developed in the pilot trial to ensure closer fidelity to the model.

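### The stated primary model omits the factors used to balance allocation; if they are prognostic, the standard error is somewhat too large and the test mildly conservative

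*Protocol*

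**What the plan says.** On the model, section 21.2 says "Regression based analyses will adjust for baseline score and take account of data clustering". No other adjustment is named for the 12-month comparison.

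On pooling, the same section says that "outcome data from both trials will be aggregated into a single data analysis at the end of the main trial". The reason given begins "As the trial protocol (other than the method of allocation) will remain consistent across pilot and main trial". No term for phase or allocation method is named.

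On balancing, the protocol has two alternative schemes for the main trial:

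- Individual allocation (section 21.2): "If there is a switch to individual randomisation after pilot, we will implement minimisation on the variables: severity of depression (i.e. BDI <20 vs >=20", together with "severity of debt (priority vs non priority); employment status (employed vs unemployed); and level of hopelessness". Section 21.2 drops this minimisation if allocation is by cluster.
- Cluster allocation (section 11): the remaining practices are "randomised to intervention or control stratified by size and the deprivation (higher vs lower) of the populations they serve".

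In the pilot, section 11 takes four practices in each of the three localities, matched on size and deprivation. That holds whichever scheme follows.

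In the analysis, section 21.2 uses the four minimisation variables only as moderators in interaction analyses. Locality appears only as a separate exploratory breakdown. A full statistical analysis plan is announced for later.

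**The concern.** When allocation is forced to balance on a factor that predicts outcome, the treatment estimate varies less from one randomisation to the next than under simple randomisation. A model that omits the factor does not see this. It leaves the factor's variance in the residual and reports a standard error that is too large. The confidence interval is then too wide, and the test rejects less often than its nominal 5%.

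Section 21.2 names an adjustment set and, in the same paragraph, names balancing factors that are not in it. Followed as written, the analysis gives away some of the precision that the allocation scheme was set up to provide. The stakes are modest: some lost precision, and an analyst's later choice of covariates that the protocol could have fixed in advance. The direction is conservative.

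**Working it through.** **1. The plan's own figure.** Section 21.1 gives a difference of 3.5, SD 9, two-sided 5% and 90% power. The formula gives n = 2 × (1.960 + 1.282)² × 9² / 3.5² = 139 per arm. The stated 135 is within 3% of this and gives 89.2% power, so the figure reproduces closely. It takes no credit for covariates; section 21.1 itself calls it likely to be conservative because of the covariance analysis.

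**2. Which factors are omitted in each branch.**

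| Part of the trial | Balanced on | Not in the stated model |
|---|---|---|
| Pilot, 120 patients, 12 practices | Practice size and deprivation, within locality | Size, deprivation, locality |
| Main trial, individual | BDI <20 v ≥20, debt severity, employment, hopelessness | Debt severity, employment, hopelessness |
| Main trial, cluster | Practice size and deprivation | Size, deprivation |

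The BDI cut is largely covered by baseline BDI, so three minimisation factors are omitted, not four.

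**3. Size under individual allocation.** Let R² be the share of the variance left after baseline BDI that the three factors explain. The documents give no value; 5, 10 and 15% are assumed. The total is 2 × 195 = 390, of whom 390 − 120 = 270 would be minimised, a fraction f = 270/390 = 0.692. Treating minimised patients as fully balanced, and ignoring clustering and pilot matching, the true variance relative to the reported one is about 1 − f·R². The true error rate is 2 × (1 − Φ(1.96/√(1 − f·R²))).

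| Assumed R² | 1 − f·R² | Reported SE too large by | True two-sided error rate |
|---|---|---|---|
| 0 | 1 | 0% | 5.0% |
| 5% | 0.965 | 1.8% | 4.6% |
| 10% | 0.931 | 3.6% | 4.2% |
| 15% | 0.896 | 5.6% | 3.8% |

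**4. Simulation of the minimised phase alone.** Assumed: 270 patients, four binary factors, a biased coin of 0.9, baseline slope 0.5, and each of the three non-BDI factors worth 0, 2, 3 or 4 BDI points.

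| Points per factor | SE, baseline only | SE, with factors | Error rate, baseline only | Error rate, with factors | Power, baseline only | Power, with factors |
|---|---|---|---|---|---|---|
| 0 | 0.95 | 0.95 | 5.7% | 5.7% | 95.7% | 95.8% |
| 2 | 0.95 | 0.93 | 4.2% | 4.8% | 96.6% | 96.9% |
| 3 | 0.95 | 0.89 | 4.1% | 5.2% | 96.8% | 97.4% |
| 4 | 0.95 | 0.85 | 3.2% | 5.6% | 97.6% | 98.5% |

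The 5.7% in the first row, where both models should give 5%, shows the simulation noise. The last row is a strong assumption: 1 − (0.85/0.95)² = 20% of the remaining variance. These rows confirm the mechanism. They do not describe the pooled trial, which also holds the pilot patients.

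**5. Effect on power.** At 135 per arm, taking no credit for baseline, an added R² of 2, 5 or 10% raises power from 89.2% to 89.8, 90.6 or 92.0%. If baseline BDI explains 25% (assumed), power goes from 95.8% to 96.1, 96.6 or 97.3%.

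**6. The phase term.** The shift from omitting phase is d × [pI/(pI + mI) − pC/(pC + mC)]. Here d is the difference in mean BDI between phases, and p and m are pilot and main numbers in the intervention (I) and control (C) arms. With 1:1 in both phases it is zero. With the pilot split 55:45 (66 v 54, assumed) and the main phase 135 v 135, the bracket is 66/201 − 54/189 = 0.0427. For d of 2 to 4 points (assumed), the shift is about 0.09 to 0.17 points, against a target of 3.5.

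**7. Cluster branch.** The mechanism is the same but acts on between-practice variance. The documents do not say how much of that practice size and deprivation explain, so no figure is given.

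**The case against.** The strongest objection is that a covariate list belongs in the statistical analysis plan, which section 21.2 announces and which was not available here. The sentence in section 21.2 excludes nothing, and that plan may add the factors. This stands as a limit: one cannot say that the final analysis will omit them. It does not remove the point, because the protocol does not leave the adjustment set open. It names one, and its own balancing factors are absent.

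Second, the harm is small and in the safe direction. In the simulation, adjusting gains at most about one point of power, and no stated sample size depends on these covariates. This stands, and it sets the weight of the point.

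Third, if clustering is handled by a practice random effect, that effect would absorb part of the practice, locality and phase variation. This stands in part. The protocol does not say how clustering is modelled, and a practice term does not deal with the patient-level factors (debt severity, employment, hopelessness).

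Fourth, the two main-trial schemes exclude each other, so no single analysis omits both sets of factors. This stands, and the fix is therefore conditional on the branch chosen.

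**Conclusion.** The point holds in a modest form. As written, the primary model leaves out the factors that the trial allocates by. If they are prognostic, the reported standard error is too large and the test conservative: about 2 to 6% and a true error rate of about 4.6 to 3.8% in the pooled individual branch, for an assumed R² of 5 to 15%. If they are not prognostic, there is no loss. The sample size stands.

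Three stronger readings are tempting and not supported:

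- A reader might infer that the error rate falls to 3.4%. That figure needs an R² of 15% and every patient minimised: 2 × (1 − Φ(1.96/√0.85)). The 120 pilot patients are not minimised, and the R² has no source in the documents.
- A reader might infer that pooling without a phase term biases the estimate systematically. Section 7 sets 1:1 allocation, so only chance imbalance can enter, and it is small (step 6).
- A reader might take "it is recognised firstly that adaptations will be required" in section 22.1 as refuting the premise for pooling. The same sentence expects no major theoretical change, and sections 7 and 22 hold the intervention fixed so that pilot data can be used. Training, manual and recruitment route may still shift, which is reason enough for a phase term and a sensitivity analysis.

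**What to change.** State in section 21.2, and carry into the statistical analysis plan, that the primary model for 12-month BDI contains:

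- arm and continuous baseline BDI;
- the balancing factors of the branch actually used: debt severity, employment and hopelessness under minimisation, or practice size and deprivation under cluster allocation;
- locality, on which the pilot was balanced;
- a pilot/main (allocation-method) term, as a guard against chance imbalance;
- practice as the cluster, with the method stated.

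Report an arm-by-phase interaction as a sensitivity analysis.

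The cost is wording and a few degrees of freedom. The variables are already collected or known at practice level.

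Adding locality to the practice strata is not proposed. With three localities, the three size bands and two deprivation levels of section 9.1, it would give 3 × 3 × 2 = 18 cells for about 45 − 12 = 33 new practices, fewer than two per cell. Adjusting for locality in the model avoids that trade-off.

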21.3 Economic evaluation

Economic analysis will be conducted from the UK NHS perspective. Incremental cost-effectiveness ratios will be generated based on the primary and secondary outcomes and will include an assessment of cost-utility as part of the cost-consequences analysis. Two time durations will be employed: a within-trial assessment and a longer-term time horizon assessment based on decision-analytic modelling- ensuring that good practice is adopted-and populated from parameter estimates derived from the trial and from information from literature sources relating to long-term effects of depression, anxiety and mental wellbeing. These time periods offer a longer duration than previous studies and will be used, alongside other sources, to arrive at more meaningful estimates of cost-effectiveness.

The costs associated with debt advice and counselling integrated with general practice (using data from CSRI and CAB process record summaries) will be estimated and compared to NICE guided treatment as usual and leaflet advice. The differences will be combined with differences in costs between intervention and control group to determine overall costs associated with the intervention. The health care resource utilisation of both groups (e.g. community based health care professional consultations, community care, anxiety and depression related prescriptions, secondary care contacts etc.) will be assessed through the completion at baseline, 4 and 12 months follow-up of the CSRI adapted for this study. These will be translated into costs using appropriate published unit costs (e.g. Curtis, 2011) ^{xviii}

The difference in overall costs between groups will be compared with differences in outcomes – as specified above – and including quality adjusted life years (QALYs). NICE recommended QALYs should be computed from EQ-5D^{xix}, and in the study we will use the recent five level update, EQ-5D-5L^{xx}.

A series of one-way sensitivity analyses will be conducted to assess the impact of parameter variation on baseline estimates of the range of incremental cost-effectiveness ratios, and a probabilistic sensitivity analysis will be undertaken to determine the extent to which the intervention can be regarded as representing value for money using the incremental cost/QALY as the metric for this assessment; measured against the NICE range of 'willingness to pay' thresholds between £20k and £30k per incremental QALY gained.

21.4 Qualitative analysis

Robust theoretical approaches to qualitative data analyse and interpretation will be employed. Narrative and constant comparative approaches will be used to develop the thematic analysis^{xxi, xxii}. Service User advisors will be involved in the process of analysing anonymised patient transcripts to provide their perspectives on data interpretation.

Semi-structured interviews with a sample of GPs and CAB advisors participating in the trial will be conducted to check fidelity and the impact of participation on attitudes and practice (using Normalisation Process Theory - NPT)^{xxiii}. Normalization Process Theory will underpin the exploration of the behavioural mechanisms that will or inhibit the routine incorporation of the intervention (GP assessment, CAB advice and shared comprehensive assessment) in everyday practice. It provides a rigorous conceptual framework to identify, describe, and understand interactions between participants' contributions (the things that they do) with the capabilities offered by the intervention - focusing attention on the intervention's workability and integration in workflow and context.

These findings will be triangulated with relevant CSRI data on appointments and process records from CAB visits and completed comprehensive assessments.

